2.7.4 Diabetes assessment

Diabetes will be assessed by the analysis of:

- TEAEs
- Change in glucose-related laboratory values over time
- Shifts from baseline in glucose control category and
- Incidence of post-baseline new onset of diabetes

Note that diabetes related tables dealing with the fasting plasma glucose parameter will require the lab sample to be taken fasting. Samples taken while the subject was not fasted will not be analyzed.

Unless otherwise specified, baseline of fasting plasma glucose will be defined as the average of Screening and Day 1 assessments. If one fasting plasma glucose value is missing (Screening or Day 1), the baseline will be based on the available data. For HbA1c, the Day 1 assessment will be considered as baseline. If missing, then the baseline will be based on the assessment at screening.

Diabetes TEAE

New onset/worsening of diabetes will be identified by the search criteria specified in [Appendix 5.4](#). The analysis will be performed for all subjects and then by baseline diabetes status. A participant will be identified as being diabetic at baseline if the medical history notes that the subject is diabetic or the baseline HbA1c value is $\geq 6.5\%$ or the baseline fasting plasma glucose is ≥ 126 mg/dL. This summary will be provided by treatment and Part.

Change in Glucose-related Laboratory Values over Time

This analysis only utilizes laboratory data (fasting plasma glucose and HbA1c). The change from baseline to the last on-treatment observation and the worst on-treatment observation will be summarized by treatment and Part, separately for fasting plasma glucose and HbA1c for all participants and then by baseline glucose control status. Baseline glucose control status will be identified separately for fasting plasma glucose and HbA1c using the values provided in the table below (note that medical history will not be considered for this analysis). Figures will also be created showing change in mean fasting plasma glucose and HbA1c values over time by baseline glucose control status.

Parameter	Baseline Glucose Control Status (Laboratory Values)
Fasting Plasma Glucose	<100 mg/dL
	≥ 100 to < 126 mg/dL
	≥ 126 mg/dL
HbA1c	<5.7%
	≥ 5.7 to $< 6.5\%$
	$\geq 6.5\%$

Shifts from Baseline in Glucose Control Category

Shifts from baseline in glucose control category will be summarized by treatment and Part in two different ways. The change from baseline to the worst-on-treatment and the last-on-treatment laboratory values will be used to classify the on-treatment glucose control category. Medical history will not be considered for this analysis.

Shift Category*	Baseline Category	Post-baseline Category**
Normal to Normal (no change)	Fasting plasma glucose <100 mg/dL AND HbA1c <5.7%	Fasting plasma glucose <100 mg/dL on two consecutive occasions AND HbA1c <5.7%
Normal to Impaired	Fasting plasma glucose <100 mg/dL AND HbA1c <5.7%	Fasting plasma glucose ≥100 and <126 mg/dL on two consecutive occasions OR HbA1c ≥5.7 and <6.5%
Normal to Diabetes	Fasting plasma glucose <100 mg/dL AND HbA1c <5.7%	Fasting plasma glucose ≥126 mg/dL on two consecutive occasions OR HbA1c ≥6.5%
Impaired to Normal	Fasting plasma glucose ≥100 and <126 mg/dL OR HbA1c ≥5.7 and <6.5%	Fasting plasma glucose <100 mg/dL on two consecutive occasions AND HbA1c <5.7%
Impaired to Impaired (no change)	Fasting plasma glucose ≥100 and <126 mg/dL OR HbA1c ≥5.7 and <6.5%	Fasting plasma glucose ≥100 and <126 mg/dL on two consecutive occasions OR HbA1c ≥5.7 and <6.5%
Impaired to Diabetes	Fasting plasma glucose ≥100 and <126 mg/dL OR HbA1c ≥5.7 and <6.5%	Fasting plasma glucose ≥126 mg/dL on two consecutive occasions OR HbA1c ≥6.5%
Diabetes to Normal	Fasting plasma glucose ≥126 mg/dL OR HbA1c ≥6.5%	Fasting plasma glucose <100 mg/dL on two consecutive occasions AND HbA1c <5.7%

Novartis SAP amendment 4	For business use only	Page 28 CKJX839C12302
-----------------------------	-----------------------	--------------------------

Diabetes to Impaired	Fasting plasma glucose ≥ 126 mg/dL OR HbA1c $\geq 6.5\%$	Fasting plasma glucose ≥ 100 and < 126 mg/dL on two consecutive occasions OR HbA1c ≥ 5.7 and $< 6.5\%$
Diabetes to Diabetes (no change)	Fasting plasma glucose ≥ 126 mg/dL OR HbA1c $\geq 6.5\%$	Fasting plasma glucose ≥ 126 mg/dL two consecutive occasions OR HbA1c $\geq 6.5\%$

*No change (Normal to Normal, Impaired to Impaired, and Diabetes to Diabetes), worsened (Normal to Impaired, Normal to Diabetes, and Impaired to Diabetes), and Improved (Impaired to Normal, Diabetes to Impaired, and Diabetes to Normal) categories will also be summarized.

***For post-baseline categories, if the post-baseline two consecutive fasting plasma glucose measurements fall in separate categories, or if only one post-baseline fasting plasma glucose measurement is available, then the post-baseline glucose control category will be defined based on the HbA1c measurement only. If HbA1c value is missing and two consecutive fasting plasma glucose measurements fall in separate categories, the lower category will be used to determine the post-baseline category.

Incidence of Post-baseline New-Onset of Diabetes

The number of participants who shift from no diabetes at baseline to post-baseline new onset of diabetes will be summarized.

The participants with no diabetes at baseline are those who had no medical history of diabetes in the medical history CRFs, had baseline HbA1c $< 6.5\%$, and had baseline fasting plasma glucose < 126 mg/dL prior to the start of study treatment.

A 4-component analysis will be utilized to detect post-baseline new onset of diabetes. The 4 components are provided below:

- Diabetic TEAEs identified by the SMQ search (see [Section 5.4](#)), or
- Post-baseline fasting plasma glucose ≥ 126 mg/dL on two consecutive occasions, or
- Initiation of anti-diabetic medication at any time post-baseline, or
- At least one post-baseline HbA1c $\geq 6.5\%$.

The number of participants who have any of the 4 components will be summarized (post-baseline new onset of diabetes) by treatment and Part.

This analysis will be performed separately for participants who had normal and impaired glucose control categories at baseline.

- Subjects with normal glucose control status at baseline are those with all the following:
 - No medical history of diabetes.
 - HbA1c $< 5.7\%$ AND fasting plasma glucose < 100 mg/dL at baseline.

Novartis SAP amendment 4	For business use only	Page 29 CKJX839C12302
-----------------------------	-----------------------	--------------------------

- Subjects with impaired glucose control status at baseline are those with all the following:
 - No medical history of diabetes.
 - HbA1c $\geq 5.7\%$ and $< 6.5\%$ (and fasting plasma glucose $< 126 \text{ mg/dL}$) OR fasting plasma glucose $\geq 100 \text{ mg/dL}$ and $< 126 \text{ mg/dL}$ (and HbA1c $< 6.5\%$) at baseline.

The time to new-onset diabetes will also be summarized by treatment and Part. Only participants without diabetes at baseline will be included in the analysis. The time (weeks) to new-onset diabetes will be calculated from the date of the first administration of study drug.

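### The SAP 2.7.4 glucose shift table uses one rule for baseline and another for post-baseline, so a participant with unchanged values can be counted as Improved and never as Worsened

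*SAP*

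**What the plan says.** All the relevant text is in SAP 2.7.4 (Diabetes assessment).

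- **Baseline glucose.** Unless stated otherwise, "baseline of fasting plasma glucose will be defined as the average of Screening and Day 1 assessments". If only one exists, it is used: "If one fasting plasma glucose value is missing (Screening or Day 1), the baseline will be based on the available data". The shift table states no other baseline.
- **Baseline HbA1c.** "For HbA1c, the Day 1 assessment will be considered as baseline", with the screening value as back-up.
- **Baseline category.** Impaired needs only "Fasting plasma glucose ≥100 and <126 mg/dL OR HbA1c ≥5.7 and <6.5"%. There is no two-occasion condition on glucose. Diabetes is built the same way, at 126 mg/dL or 6.5%.
- **Post-baseline category.** Glucose must fall in the category twice running. Normal, for example, is "Fasting plasma glucose <100 mg/dL on two consecutive occasions AND HbA1c <5.7"%.
- **Post-baseline fallback** (footnote to the table). The trigger is "if the post-baseline two consecutive fasting plasma glucose measurements fall in separate categories, or if only one post-baseline fasting plasma glucose measurement is available", and "then the post-baseline glucose control category will be defined based on the HbA1c measurement only". If HbA1c is missing and the pair is split, "the lower category will be used to determine the post-baseline category".

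Impaired to Normal, Diabetes to Impaired and Diabetes to Normal are then pooled as Improved. The shifts are tabulated for the last and for the worst on-treatment value, by treatment and Part.

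**The concern.** A shift table is informative only if the same measurements give the same category at both ends. Here both ends normally rest on two fasting values, but they are read differently. At baseline, one higher value can lift the mean over a cut-point. Afterwards, the same pair is treated as discordant, and its glucose information is discarded in favour of HbA1c. A participant whose glucose has not moved can then appear to have improved.

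New-onset diabetes and worsening glycemic control is a named safety topic (SAP 2.7.1), and the DMC monitors it (Protocol 10.2.3). A table meant to reveal worsening should not have a built-in lean toward improvement. In Part 2 everyone receives inclisiran while baseline stays before the first dose (SAP 2.1.1), so no concurrent control shows the same artefact. In Part 1 the control arm is about 4 of 12 participants (2:1 randomization).

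**Working it through.** The documents give no figure to reproduce, so the check applies the rules as written.

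**Rules.** Let G be the glucose category (cut-points 100 and 126 mg/dL) and H the HbA1c category (5.7% and 6.5%). Let a and b be the two fasting values. Where the OR definitions overlap, the SAP gives no precedence, and the higher category is taken.

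- Baseline = the higher of G(mean of a and b) and H.
- Post-baseline, if G(a) = G(b): the higher of G(a) and H.
- Post-baseline, if G(a) and G(b) differ: H, or the lower of G(a) and G(b) if HbA1c is missing.

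**Direction.** Give a participant the same a, b and HbA1c at both times. If G(a) = G(b), the mean lies between a and b, so both rules agree. If the pair is split, the post-baseline result is H, which cannot exceed the higher of G(mean) and H. With HbA1c missing it is the lower glucose category, which cannot exceed G(mean). Unchanged values can therefore move down but never up.

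**Examples, identical values at both times.**

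| Fasting glucose (mg/dL) | Baseline figure | HbA1c | Baseline | Post-baseline |
|---|---|---|---|---|
| 96, 106 | (96+106)/2 = 101 | 5.4% | Impaired | Normal |
| 118, 136 | (118+136)/2 = 127 | 5.4% | Diabetes | Normal |
| 120, 134 | 127 | 6.0% | Diabetes | Impaired |
| 98, 104 | 101 | missing | Impaired | Normal |
| 104 only | 104 | 5.4% | Impaired | Normal |
| 104, 104 | 104 | 5.4% | Impaired | Impaired |
| 94, 102 | 98 | 5.4% | Normal | Normal |
| 98, 104 | 101 | 5.8% | Impaired | Impaired |

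The first five are reported as Improved and the last three as no change. The 96/106 result does not depend on the precedence assumption.

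**Enumeration.** Take all integer pairs from 70 to 160 mg/dL with HbA1c 5.4%, 6.0%, 6.6% or missing: 91 × 91 × 4 = 33,124 profiles. With HbA1c 5.4% there are 5,480 split pairs: 4,550 Improved, 930 unchanged, none Worsened. Among split pairs within 90-110 mg/dL, 110 of 220 are Improved. With HbA1c 6.6% none shifts. With one rule at both times, 0 of 33,124 change category. These are counts of profiles, not probabilities.

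**Likely size.** This needs assumptions from outside the documents: mean fasting glucose 92-98 mg/dL, between-person SD 6-8, within-person SD 5-8, HbA1c below 5.7% in everyone, no true change, two baseline values and six Part 1 post-baseline values (Days 30, 90, 150, 270, 330 and 360 in Protocol Table 8-1). Last-on-treatment uses the final two values. Worst-on-treatment takes the highest category over consecutive pairs.

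| Shift table | Rule | Improved | Worsened |
|---|---|---|---|
| Last | SAP | 8-25% | 2.5-8% |
| Last | Same rule at both times | equal to Worsened | equal to Improved |
| Worst | SAP | 4-11% | 8-21% |
| Worst | Same rule at both times | 2-5% | 11-33% |

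For the last value, 8/2.5 = 3.2 and 25/8 = 3.1, so about 3 to 1. For the worst value, the ends of the ranges give 1 - 8/11 = 27% and 1 - 21/33 = 36% fewer counted as worsened. Across scenarios the reduction is about a quarter to two-fifths.

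With an assumed true rise of 10 mg/dL, the SAP rules also record fewer worsened participants than one rule does, for example 33% against 42%.

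**The case against.** **Confirmation after baseline is sound practice.** Protocol 8.4.4.5 asks for two consecutive values of at least 126 mg/dL before new-onset diabetes is reported on glucose. This stands, and it is a reason to keep the post-baseline rule and change the baseline. Classifying post-baseline on a mean would make Diabetes in this table differ from the two-consecutive-value criterion in the new-onset analysis.

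**Other analyses cover the same ground.** SAP 2.7.3 and 2.7.4 also provide continuous change in glucose and HbA1c, an HbA1c shift table, counts of notable glucose values, diabetes adverse events, the four-component new-onset analysis and full listings. In about 12 participants a misclassified case can be found by eye. This stands, and it keeps the point minor.

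**In Part 1 the same rule applies to both arms.** That is true, but about 4 placebo participants are too few to show the artefact reliably, and Part 2 has no control.

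**Some stronger readings go too far.**

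- A reader might infer that anyone with unchanged values is counted as improved. The examples show otherwise: the values must straddle a cut-point (or be single), the baseline figure must lie in a higher category than the fallback gives, and HbA1c must be in a lower category or missing.
- A reader might infer that both tables lean toward improvement. The worst-on-treatment table does not. With no true change, a lower worsened count there also means fewer false alarms; only the true-rise example bears on real worsening.
- A reader might infer that the baseline mean materially depletes the at-risk set for new-onset diabetes. Exclusion on glucose needs a mean of at least 126 mg/dL with no diabetes history and HbA1c below 6.5%. At the most extreme assumptions (mean 98, both SDs 8) the chance is about 0.2%, or 0.002 × 12 = about 0.02 participants.

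**Conclusion.** The mismatch is in the SAP text, and its direction follows from the rules without any assumption: for unchanged values it can produce Improved and cannot produce Worsened. No other section corrects it.

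Its size rests on glucose distributions that the documents do not give and on HbA1c below 5.7% in everyone. On those terms the last-on-treatment excess of improved over worsened is roughly 8 - 2.5 = 5.5 to 25 - 8 = 17 percentage points, or about 0.7 to 2 of 12 participants. The shortfall in worst-on-treatment worsening is about a quarter to two-fifths. The effect would be smaller where HbA1c is already in the same category as glucose or a higher one.

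This is a minor correction to a descriptive safety table. No hypothesis test depends on it, the primary LDL-C endpoint is untouched, and the documents do not support treating it as a material flaw in the new-onset diabetes analysis.

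**What to change.** In SAP 2.7.4, for the glucose control shift table only, classify baseline by applying the post-baseline two-value rule to the Screening and Day 1 pair. Use the same fallback: baseline HbA1c alone if the pair splits or only one value exists, and the lower glucose category if the pair splits and HbA1c is missing. The opening phrase of the baseline definition already allows such an exception. Keep the average as baseline for the continuous change summaries.

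The cost is SAP wording and one derivation. No new data are needed, because fasting glucose and HbA1c are in the chemistry panels scheduled at both Screening and Day 1 (Protocol Tables 8-1 and 8-3). The downside is that baseline glucose no longer contributes to the category when the pair splits or one value is missing.

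If the present rule is kept, a footnote should state that the two ends are classified differently, and the affected participants should be listed.

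### SAP 2.7.4 glucose shift table: with HbA1c below 5.7%, a fasting pair of 120/130 mg/dL is classed Normal although the milder pair 120/120 is Impaired

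*SAP*

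**What the plan says.** The rules are in SAP 2.7.4, in the part on shifts from baseline in glucose control category.

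- **Normal after baseline** needs both fasting values below 100 mg/dL and HbA1c below 5.7%.
- **Impaired after baseline** is "Fasting plasma glucose ≥100 and <126 mg/dL on two consecutive occasions OR HbA1c ≥5.7 and <6.5" (per cent).
- **Diabetes after baseline** is "Fasting plasma glucose ≥126 mg/dL on two consecutive occasions OR HbA1c ≥6.5" (per cent).
- **Discordant fasting pair, or only one fasting value:** under the table footnote, "then the post-baseline glucose control category will be defined based on the HbA1c measurement only".
- **Discordant pair with HbA1c missing:** "the lower category will be used to determine the post-baseline category".
- **Which values are used:** "The change from baseline to the worst-on-treatment and the last-on-treatment laboratory values will be used to classify the on-treatment glucose control category".
- **Summary of direction:** besides no change and worsened, "Improved (Impaired to Normal, Diabetes to Impaired, and Diabetes to Normal) categories will also be summarized".

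Two neighbouring parts of SAP 2.7.4 treat the categories as exclusive at baseline. The diabetes TEAE analysis calls a participant diabetic if HbA1c is at least 6.5% or fasting glucose is at least 126 mg/dL (or by medical history). In the new-onset analysis, the definition that begins "Subjects with impaired glucose control status at baseline are those with all the following" admits a participant on one marker only if the other is below its diabetes cut-off. The shift table carries no such condition.

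**The concern.** A shift table should not give a participant with worse values a better category. The discordant-pair rule does so in one situation: both fasting values are abnormal, one lies on each side of 126 mg/dL, and HbA1c is normal. The participant is then called Normal, although neither fasting value is below 100 mg/dL. The table can show an improvement that the fasting values do not support, or miss a worsening. The rule is explicit, so a programmer who follows the text will reproduce the error.

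Diabetes is one of the SAP's listed safety topics, and the columns are small. With about 12 participants randomized 2:1, roughly 12 × 1/3 = 4 start on placebo, so one misclassified participant is about a quarter of that column.

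Separately, because Impaired and Diabetes are both OR rules, some participants satisfy both, and the table does not say which applies.

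**Working it through.** The plan gives no figure to reproduce. The check applies the written rule to every combination.

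**Inputs (SAP 2.7.4).** Fasting glucose: N below 100, I 100 to below 126, D 126 mg/dL or more. HbA1c: N below 5.7%, I 5.7% to below 6.5%, D 6.5% or more.

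**Rule as written.** If the two fasting values share a category, apply the Normal (AND), Impaired (OR) and Diabetes (OR) definitions. If they differ, the category is that of HbA1c. If HbA1c is missing as well, it is the lower fasting category.

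**Step 1: worked cases.**

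| Fasting pair (mg/dL) | HbA1c | Category as written |
|---|---|---|
| 90/90 | 5.5% | Normal |
| 90/130 | 5.5% | Normal (HbA1c only) |
| 120/120 | 5.5% | Impaired |
| 120/130 | 5.5% | Normal (HbA1c only) |
| 130/130 | 5.5% | Diabetes |
| 120/130 | missing | Impaired (lower category) |
| 120/130 | 6.0% | Impaired (HbA1c only) |
| 120/130 | 6.6% | Diabetes (HbA1c only) |

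At HbA1c 5.5%, raising one value of 120/120 to 130 lowers the category, and raising both raises it. A normal HbA1c result also makes 120/130 better than no HbA1c result at all.

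**Step 2: all complete-data combinations.** There are 3 × 3 × 3 = 27 (first fasting, second fasting, HbA1c). The test is that a combination at least as bad in every component must not get a lower category. With overlaps resolved Diabetes first, it fails for 2 of 27: I/D/N and D/I/N, both Normal, against I/I/N, which is Impaired. At HbA1c of 5.7% or more there is no reversal.

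**Step 3: effect on the direction of shift.** There are 9 baseline combinations (fasting × HbA1c). With Diabetes first these are 1 Normal, 3 Impaired and 5 Diabetes. Crossing them with the 2 faulty pairs gives 9 × 2 = 18. If the faulty pairs were Impaired instead of Normal:

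- Impaired baseline: 3 × 2 = 6 move from improved to no change.
- Normal baseline: 1 × 2 = 2 move from no change to worsened.
- Diabetes baseline: 5 × 2 = 10 are improved either way.

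So the direction changes in 6 + 2 = 8 of 18. Of the 6, the 4 from baselines with Impaired HbA1c (fasting/HbA1c N/I and I/I) do show HbA1c falling to normal. The 2 from baseline I/N show neither component moving to a better category.

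**Step 4: overlap.** After baseline, I/I/D and D/D/I meet both definitions (2 of 27). At baseline, I/D and D/I do (2 of 9). Example: baseline fasting 120 mg/dL and HbA1c 6.0% (Impaired only), then 130/130 with HbA1c 6.0%. This fits both Impaired to Diabetes (worsened) and Impaired to Impaired (no change). With baseline fixed as Diabetes first, the post-baseline order matters in 3 × 2 = 6 combinations (worsened or no change) and 5 × 2 = 10 (no change or improved). That is 16 of 27 × 9 = 243.

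All these are counts of combinations, not weighted by how likely each is.

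**The case against.** **HbA1c is a reasonable tie-breaker.** It is, where one of the two fasting values is normal, and that use is not challenged. Nor are the two-occasion requirement or the single-value rule. But the SAP does not let a normal HbA1c override abnormal fasting values in general: 120/120 stays Impaired despite it. It overrides only the worse, discordant pair. The reversal stands.

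**The improvement is not always false.** This is correct. A reader might infer that every improved entry from a faulty pair is spurious. In 4 of the 6 affected combinations HbA1c really did return to normal. The claim is fully supported only for the 2 that start from a baseline impaired on fasting glucose alone.

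**The intended order is clear from the section.** This largely stands. A reader might infer that any order is equally open, or that the SAP contradicts itself. The diabetes TEAE and new-onset analyses both rank Diabetes first, so the 16 order-dependent combinations matter only if a programmer goes against them. A disagreement with the new-onset table would be weak evidence, because that table counts events at any time and also uses medical history, adverse events and medication. What remains is that the shift table does not state its order, and that selecting worst or last values does not rank categories.

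**How often will it happen?** A reader might want a percentage. Any such figure depends almost wholly on an assumed mean fasting glucose, which neither document gives, so none is quoted.

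**Conclusion.** The discordant-pair rule is wrong as written for one configuration: both fasting values at or above 100 mg/dL, one on each side of 126 mg/dL, with HbA1c below 5.7%. That is 2 of 27 complete-data combinations. It can turn no change into improved, or worsened into no change. The missing order between Impaired and Diabetes is a secondary point, mainly a clarification.

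The conclusion rests on a literal reading of the table and footnote and, for the shift directions, on ranking Diabetes first at baseline. Its frequency in this trial is unknown. It touches one descriptive safety table in about 12 participants. The documents do not support a wider claim: new-onset diabetes has its own rule, and the notable-value counts, the glucose and HbA1c change summaries and the participant listings do not use this classification. Severity: minor.

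**What to change.** Replace the discordant-pair rule in the SAP 2.7.4 table footnote with:

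> If two consecutive fasting values fall in separate categories, the lower of the two is the fasting category; the post-baseline category is the worse of the fasting category and the HbA1c category (fasting category alone if HbA1c is missing).

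Add:

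> At baseline and post-baseline, categories are assigned in the order Diabetes, Impaired, Normal; the first one met applies.

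> For the worst-on-treatment table, the worst category over all consecutive on-treatment pairs is used.

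The last sentence is needed because the SAP does not say whether worst refers to a value, a pair or a category.

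For any given two fasting values and HbA1c, this changes 4 of the 27 cells: I/D/N and D/I/N become Impaired, and I/I/D and D/D/I become Diabetes only. The ordering failures fall from 2 to 0. The single-fasting-value rule stays as it is. Two situations with HbA1c missing remain unclassified, as now: both fasting values below 100 mg/dL, and only one post-baseline fasting value.

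The cost is three sentences in the SAP and the matching programming of this table. No new data are needed.

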2.1.1 General definitions

Study Day

Study day will be defined as the number of days since the date of first dose of double-blind treatment. The date of first dose of double-blind treatment will be defined as Day 1 and the day before the first dose of study drug will be defined as Day -1.

Therefore, for a particular date, study day will be calculated as follows:

For dates on or after the first date of double-blind treatment,

Study day = Assessment date – Date of first dose of double-blind treatment + 1;

For dates prior to the first date of double-blind treatment,

Study day = Assessment date – Date of first dose of double-blind treatment.

In case, participant has been randomized but has not received double-blind treatment then randomization visit day will be considered as Day 1.

Baseline definition

In general, for both Part 1 and Part 2, baseline value is defined as the last measurement collected on or prior to the first dose of double-blind treatment.

Post-baseline measurement

Post-baseline values are defined as those measurements that were collected after the first dose of double-blind treatment.

When change from baseline is of interest the following formula will be used for each scheduled visit and time-point where baseline and post-baseline values are both available:

Absolute change from baseline = post-baseline value – baseline value.

Percent change from baseline = (post-baseline value – baseline value) / baseline value*100.

LDL-C to be used in analysis

The endpoints involving LDL-C will use the beta quantification (ultracentrifugation) LDL-C for all subjects. In cases where beta quantification (ultracentrifugation) LDL-C values are missing and calculated LDL-C is available, the calculated LDL-C will be used for analysis purposes.

VLDL-C

The endpoints involving VLDL-C will use the beta quantification (ultracentrifugation) VLDL-C for all subjects. In cases where beta quantification (ultracentrifugation) VLDL-C values are missing and calculated VLDL-C is available, the calculated VLDL-C will be used for analysis purposes.

Discontinuation visit mapping

For patients who discontinued the study and come to site for an early exit (EE) visit, the EE visit will be mapped to the next scheduled visit. The mapping details can be found as below:

Table 2-1 Visit mapping

Status	Last attended scheduled visit prior to EE		Mapped visit for EE	
Visit day	Visit name	Visit day	Visit name	Visit day
Discontinued (Early exit)	1	Day 1	90	Day 90

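### New-onset diabetes is counted by Part against one pre-Day 1 baseline, so a Part 1 laboratory case that persists is counted again as new in Part 2

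*SAP*

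**What the plan says.** **Baseline.** SAP 2.1.1 sets one baseline for the whole study, tied to the start of the double-blind period: "for both Part 1 and Part 2, baseline value is defined as the last measurement collected on or prior to the first dose". SAP 2.7.4 refines it for the diabetes analyses: "baseline of fasting plasma glucose will be defined as the average of Screening and Day 1 assessments", and "For HbA1c, the Day 1 assessment will be considered as baseline". If a value is missing, the remaining one is used. Nothing resets the baseline at Day 360.

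**Who is at risk.** "The participants with no diabetes at baseline are those who had no medical history of diabetes in the medical history CRFs", and whose HbA1c was below 6.5% and fasting glucose below 126 mg/dL "prior to the start of study treatment".

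**What counts as an event.** Any one of four components is enough:
- a diabetic TEAE found by the search criteria;
- fasting glucose of 126 mg/dL or more on two consecutive occasions;
- start of anti-diabetic medication after baseline;
- "At least one post-baseline HbA1c" of 6.5% or more.

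**How it is reported.** "The number of participants who have any of the 4 components will be summarized (post-baseline new onset of diabetes) by treatment and Part". Time to onset is also split by treatment and Part, with this origin: "The time (weeks) to new-onset diabetes will be calculated from the date of the first administration of study drug".

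**Part 2 population and columns.** SAP 2.2 defines the OAS as everyone who entered Part 2 and was dosed in it. SAP 2.1 shows Part 2 results as inclisiran-inclisiran and placebo-inclisiran, with a total column where needed.

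**The concern.** Incidence in a second period needs an at-risk set defined at the start of that period. Here the set is fixed before Day 1 and used again for Part 2, and no rule limits a participant to a first occurrence. Two of the four components describe a laboratory state that can last, so the same onset can be reported as new in both Parts.

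What is at stake is how the Part 2 safety table reads. A case that began during placebo treatment would be listed as new onset in a period when every participant is assigned inclisiran. A case that began on inclisiran in Part 1 would show in both Parts. With about 12 participants, a single case determines what the table shows.

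The time origin adds to this. In the placebo-inclisiran group, a Part 2 onset time measured from the first study drug includes the placebo year. For a recounted case, the SAP does not say which date would be the Part 2 onset date.

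**Working it through.** The plan gives no diabetes rate or target and bases the sample size on feasibility, so there is no stated figure to reproduce. The check applies the rules as written.

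**1. Is the laboratory state measured again in Part 2?** Yes. Protocol Table 8-3 puts HbA1c and fasting glucose in both the full and the limited chemistry panel. Table 8-1 schedules one of these panels on Days 450, 510, 630 and 720, giving four scheduled values after the Day 360 dose.

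**2. Does each component carry a Part 1 case forward?**

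| Component | Carried into Part 2? | Basis |
|---|---|---|
| HbA1c of 6.5% or more | Yes, if any Part 2 value is still that high | One value is enough, and it need not be the first such value |
| Two consecutive fasting glucose values of 126 mg/dL or more | Yes, if such a pair recurs in Part 2 | No first-occurrence condition |
| TEAE | Not if unchanged | SAP 2.7: a Part 2 TEAE must start after, or worsen in severity after, Day 360 dosing |
| Anti-diabetic medication | Unclear | SAP 2.7.4 speaks of initiation after baseline; the concomitant-therapy row of SAP Appendix 5.3 counts continuing medication in both Parts, but does not mention this component |

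**3. Three hypothetical participants, none diabetic at baseline**

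| Course | As written | If Part 1 cases leave the Part 2 set |
|---|---|---|
| A. HbA1c reaches 6.5% in Part 1 and stays at or above it | Part 1 and Part 2 | Part 1 only |
| B. Diabetic and treated in Part 1; HbA1c and glucose below threshold throughout Part 2; no new or worse TEAE | Part 1 only, or both Parts if continuing medication counts | Part 1 only |
| C. First onset in Part 2 | Part 2 only | Part 2 only |

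**4. How easily is a Part 1 case recounted through HbA1c alone?** Let p be the chance that any one Part 2 sample is 6.5% or more. The documents give no value, so p is an assumption, and the four samples are treated as independent. The chance of at least one such value is 1 − (1 − p)^4:

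| p | Chance of recount |
|---|---|
| 0.10 | 34.4% |
| 0.25 | 68.4% |
| 0.50 | 93.8% |
| 0.75 | 99.6% |
| 0.90 | above 99.9% |

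**5. Effect of one persisting case.** Twelve participants at 2:1 give 12 × 2/3 = 8 and 12 × 1/3 = 4. Assume all enter Part 2 and none is diabetic at baseline.

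| Case arises on | Part 2 group, as written | Part 2 group, corrected | Part 2 total, as written | Part 2 total, corrected |
|---|---|---|---|---|
| Placebo | 1/4 (25%) | 0/3 | 1/12 (8.3%) | 0/11 |
| Inclisiran | 1/8 (12.5%) | 0/7 | 1/12 (8.3%) | 0/11 |

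**6. Time origin.** Day 360 − Day 1 = 359 days, and 359 / 7 = 51.3 weeks. On the planned schedule, a true Part 2 onset in placebo-inclisiran is reported about 51 weeks longer than the time since first inclisiran.

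**7. Would another table put it right?** The diabetes row of SAP Appendix 5.3 lists Part 1 and Part 2 analyses and leaves the combined column empty. No planned combined count shows each participant once.

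**The case against.** The strongest defence is that the AE route already covers this. Protocol 8.4.4.5 asks investigators to report new onset of diabetes as an AE at the same laboratory thresholds, and SAP 2.7.4 has a separate TEAE summary by treatment and Part. An unchanged Part 1 event does not reappear there. That is correct, but it does not alter the four-component count. It shows that the SAP blocks carry-over for AEs and has no matching rule for the laboratory components of the same composite.

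A second defence is that new onset implies a first occurrence, and that measuring time from the first study drug suggests one onset date per participant. The authors may have meant this. However, the SAP defines the shift from a pre-Day 1 baseline and counts any component by Part, so a programmer following the text would recount a persisting case.

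Several stronger readings are tempting, and the documents do not support them:
- **Every Part 1 case is counted twice.** Recounting requires a component to be met in Part 2; course B above may not be recounted.
- **Placebo cases are shown as inclisiran cases.** The column is labelled placebo-inclisiran, the case also stands under placebo in Part 1, and laboratory data are listed by participant and visit. Only a Part 2 total would merge the groups.
- **The Part 2 figure is simply prevalence.** Participants diabetic at baseline are excluded, and controlled or resolved cases can drop out.
- **The DMC would be misled.** DMC outputs have their own charter, SAP and shells.
- **The table will overstate a rate by 25 percentage points.** For this analysis SAP 2.7.4 specifies a number of participants and mentions no percentage.

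It is also fair to say that time from Day 1 is explicitly defined, and that its offset in the placebo-inclisiran group is known and nearly constant.

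**Conclusion.** The concern holds in limited form. Under SAP 2.7.4 as written, a participant who first meets the HbA1c or fasting glucose component in Part 1 is counted again as new onset in Part 2 if that component is still met there. An unchanged TEAE does not cause a recount. Medication started in Part 1 may or may not, because the text does not settle it.

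The size is one extra Part 2 case for each persisting Part 1 case. The fractions above rest on an exact 8/4 split, full entry into Part 2 and no diabetes at baseline; the percentages also suppose that one is reported. The documents give no event rate for this population. The protocol's background section reports no difference from placebo in new or worsening diabetes in the adult programme, so there may be no Part 1 case, and then no double count.

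The effect is confined to safety tables in the clinical study report. The primary endpoint is unchanged. It is still worth correcting, because new-onset diabetes is a named safety topic and one case would determine what the table shows.

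**What to change.** Make three changes in SAP 2.7.4:

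1. For Part 2, include only OAS participants with no diabetes at baseline and none of the four components met up to Day 360 dosing.
2. Count each participant once, in the Part where the first component occurs. Together with the first change, this also settles the medication question for Part 2, because anyone who started anti-diabetic medication in Part 1 has already left the at-risk set.
3. For Part 2 onset in placebo-inclisiran, report time from the Day 360 dose as well as from Day 1.

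The cost is a few sentences, a changed denominator in the new-onset table and one added time summary. No new data are needed. The downside is a slightly smaller Part 2 denominator whenever a Part 1 case has occurred.
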